 - iii. COPD assessment - year of diagnosis, home use of supplemental oxygen, self-reported history of spirometry being conducted, number of hospitalizations for COPD exacerbations in the year prior to admission, number of courses of antibiotics and/or steroids for COPD exacerbations in the year prior to admission. For protocol Option 1 this will be collected via self-report utilizing a questionnaire during the hospitalization. For protocol Option 2, this information will be obtained

after discharge and phone consent. For protocol Option 3 as much of this information as possible will be collected from review of the EMR.

- iv. Most recent forced expiratory volume (FEV1) and forced vital capacity (absolute and percent predicted) from EMR if documented in the 3 years prior to admission
- v. Comorbidity assessment to include cardiovascular disease and risk: history of hypertension, hyperlipidemia, coronary artery disease, prior MI, heart failure (ejection fraction prior to admission if available), percutaneous coronary intervention (PCI), coronary artery bypass grafting (CABG), peripheral vascular disease, stroke, diabetes mellitus, cirrhosis, asthma, obstructive sleep apnea, depression, anxiety, end-stage renal disease, cancer (type), organ transplantation (type)
- vi. Respiratory medication use on admission
- vii. Cardiovascular medication use on admission
- viii. Assessment of in hospital MI treatment: thrombolytics, PCI, CABG
- ix. Diagnosis of ST elevation MI (STEMI) or non-ST elevation MI (NSTEMI)
 - x. Initial post MI ejection fraction from inpatient echocardiogram
 - xi. Length of hospital stay
 - xii. Length of ICU stay
 - xiii. Need for intubation
 - xiv. Cardiogenic shock during hospital stay
 - xv. Discharge cardiovascular medications
 - xvi. Discharge disposition
- b. Phone calls (Option 1 only) and EMR review at 3 and 6 months
 - i. Vital status
 - ii. Date and cause of death if applicable
 - iii. Interval history of hospitalization and primary diagnosis (all events will be captured but hospitalizations for COPD exacerbations, recurrent MI, revascularization, or heart failure will be specifically queried)
 - iv. Interval history of treatment with steroids or antibiotics for exacerbations of COPD
 - v. Beta-blocker use and reason for discontinuation, if applicable Medical records will be collected for all admissions

g) Analytic and Statistical considerations.

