- a. Analysis plan for Aim 1. The primary objectives of Aim 1 are to determine the number of admissions per year for AMI at our participating institutions and the prevalence of COPD in that population. These prevalence estimates will be calculated as a simple fraction. We will also compare the clinical characteristics of COPD patients discharged on a beta-blocker versus those not discharged on a beta-blocker using t-tests or chi-square tests (or Fisher's exact tests) as appropriate.
- b. Analysis plan for Aim 2. For the primary analysis we will compare the risk of death or all-cause hospitalization at 6 months for patients with AMI and COPD who were discharged alive on beta-blockers to that of patients not

discharged on beta-blockers. Secondary analyses will include comparisons of rates of hospitalization for COPD exacerbations, rates of hospitalization for recurrent MI or revascularization or heart failure, and rates of treatment with steroids and/or antibiotics for exacerbations. The primary analysis will be based on adjusted Kaplan–Meier survival curves that describe the probability remaining alive and out of hospital in those discharged versus not discharged on beta-blockers, while adjusting for the inverse probability of treatment weighting (IPTW) to reduce confounding. For all time-to-event analyses, the start time will be when the participant is discharged from the hospital.

Participants will be censored at 6 months post-discharge if no event occurred. The comparison of clinical characteristics between treatment groups conducted in aim 1 will be used to inform the calculation of the IPTW. We will use the adjusted log-rank test to compare the two curves. As secondary analyses, we will use both IPTW and adjusted Cox proportional-hazards models to assess the association between the beta-blocker prescription and death or re-hospitalization. Adjusted models will also include the covariates of race, sex, baseline age, smoking status, number of hospitalizations for COPD during the previous year, use of supplemental oxygen, presence of ejection fraction <40% at discharge. Assuming adequate frequencies between groups, we will stratify the models by beta-blocker use at the time of admission, presence of asthma, STEMI vs. NSTEMI, and site. Rates of exacerbation will be analyzed by IPTW negative binomial regression models and will be used to compare annualized rates of hospitalization.

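### Atrial fibrillation or flutter is not named among the baseline data, so the weighted primary analysis cannot directly balance or check it; the documents do not fix the direction or size of any resulting bias

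*Combined protocol and SAP*

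**What the plan says.** Section 4(f), item a.v, asks for "Comorbidity assessment to include cardiovascular disease and risk: history of hypertension, hyperlipidemia, coronary artery disease, prior MI, heart failure", then coronary procedures, then "peripheral vascular disease, stroke, diabetes mellitus, cirrhosis, asthma, obstructive sleep apnea, depression, anxiety, end-stage renal disease", then cancer and organ transplantation. That is 18 entries, and none is AF, flutter or another arrhythmia. Items i to xvi contain no other field for rhythm. The nearest are "Cardiovascular medication use on admission", "Discharge cardiovascular medications" and the ejection fraction entries.

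Section 4(g), item b, bases the primary analysis on adjusted Kaplan–Meier curves "while adjusting for the inverse probability of treatment weighting (IPTW) to reduce confounding", compared by an adjusted log-rank test. It fixes no covariate list for the weights: "The comparison of clinical characteristics between treatment groups conducted in aim 1 will be used to inform the calculation of the IPTW". For the secondary Cox models it says: "Adjusted models will also include the covariates of race, sex, baseline age, smoking status, number of hospitalizations for COPD during the previous year", followed by supplemental oxygen and low ejection fraction at discharge. Where frequencies allow, the models are stratified by beta-blocker use at admission, asthma, type of MI and site. AF is in neither list.

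**The concern.** AF is a plausible reason to prescribe a beta-blocker apart from the infarction, and plausibly a marker of higher risk of death and readmission. A variable with both properties is a confounder by indication. The weights are to be informed by a comparison of collected characteristics, so a field that was not abstracted cannot show up as imbalanced, enter the propensity model or be checked after weighting.

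At stake is the balance the study is meant to assess. The primary endpoint includes all-cause hospitalization, and Sections 1 and 2 motivate the study by a hospitalization signal in the earlier randomized trial. If AF is more common among treated patients and carries more risk, it would hide part of a benefit or add to an apparent harm.

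**Working it through.** **1. The plan's own figure.** Inputs from Section 4(g), item c: 6-month risk 25% on and 37.5% off beta-blocker, two-sided 5% (sidedness is not stated, but two-sided reproduces Table 1), power 80%. With a proportion p treated:

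- HR = ln(1 − 0.25) / ln(1 − 0.375) = 0.612
- events d = (1.96 + 0.842)² / [p(1 − p)(ln HR)²]
- N = d / [0.25p + 0.375(1 − p)]

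At p = 0.65, d = 143.2 and N = 143.2 / 0.29375 = 487.4, so 488 as in Table 1. The same formula reproduces all 44 cells to within one patient. The consent target also reproduces: 500 / 0.875 = 571. Table 1 is sound on its own terms; it is used here only to size a bias.

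**2. Bias from one unmeasured binary confounder.** Let a1 and a0 be the AF prevalence in treated and untreated patients, and R the risk ratio of AF for the endpoint. Then

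bias factor = [1 + a1(R − 1)] / [1 + a0(R − 1)].

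None of the AF inputs is in the documents. Assumed ranges: prevalence 12–25%; 80–90% of AF patients and 60–70% of the others discharged on a beta-blocker; R from 1.3 to 1.8.

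- Lowest corner (12%; 80% v 70%; R 1.3): treated 71.2%, a1 = 0.096/0.712 = 0.135, a0 = 0.024/0.288 = 0.083, factor 1.0404/1.0250 = 1.015.
- Highest corner (25%; 90% v 60%; R 1.8): treated 67.5%, a1 = 0.225/0.675 = 0.333, a0 = 0.025/0.325 = 0.077, factor 1.2667/1.0615 = 1.19.
- Central case (18%; 90% v 70%; R 1.5): treated 0.18 × 0.90 + 0.82 × 0.70 = 73.6%, a1 = 0.162/0.736 = 0.220, a0 = 0.018/0.264 = 0.068, factor 1.1101/1.0341 = 1.073.

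**3. Effect on power in the central case**, with N = 500 and p = 0.736. Power = Φ(|ln HR| √[p(1 − p)d] − 1.96).

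- No bias: d = 500 × (0.736 × 0.25 + 0.264 × 0.375) = 141.5; 0.491 × √(0.1943 × 141.5) − 1.96 = 0.61; power 73%.
- With bias, untreated risk held at 37.5%: treated risk 0.25 × 1.073 = 0.268, HR 0.665, d = 148.3; 0.408 × √(0.1943 × 148.3) − 1.96 = 0.23; power 59%.
- Shifting both groups instead, so that the population-average risks stay at 25% and 37.5%: divide by 1 + 0.18 × 0.5 = 1.09, giving 0.25 × 1.1101/1.09 = 25.5% and 0.375 × 1.0341/1.09 = 35.6%; HR 0.668; power about 56%.

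**4. A second set of assumptions**, using odds ratios for prescribing. With prevalence 10–20%, prescribing odds ratio 1.5–3 and R 1.3–2.0, the factor is about 1.01 to 1.15 across 45–85% treated. At 65% treated, power falls from 81% to between 79% (mildest case) and 48% (strongest).

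**5. When the sign changes.** If AF does not alter prescribing, a1 = a0 and the factor is 1. With 15% prevalence, prescribing odds ratio 0.7, R 1.6 and 65% treated, a1 = 0.134 and a0 = 0.180, so the factor is 1.080/1.108 = 0.975. A true risk ratio of 0.667 then appears as 0.650, and the benefit is overstated.

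**The case against.** The strongest reply is that neither direction nor size comes from the documents. They say nothing about how common AF is in this cohort, whether it raises prescribing, or what it does to outcome. That stands, and step 5 shows that the bias vanishes or reverses if AF does not raise prescribing.

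A reader might infer that a true benefit will be understated. The documents do not support this. The selection concern in Section 2, raised about an earlier study, is that healthier patients may have received beta-blockers, which would overstate benefit. Section 2 also describes the drugs being withheld because of COPD. AF is one component of a residual confounding whose net sign is unknown.

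A reader might also infer that the weights cannot balance AF at all. That is too strong. Admission cardiovascular drugs, beta-blocker use at admission, heart failure and stroke are available to the weights, because no closed propensity list is given, and may balance part of pre-existing AF. They do not clearly cover AF first arising in the index stay. Stratification by admission beta-blocker use is conditional on frequencies and is described for the models.

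The wording of item a.v does not clearly close the list, and the case report form is not part of the documents. So the supportable statement is that AF is not named, not that it will never be recorded.

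Finally, it is tempting to read the power loss at the 65% treated column of Table 1, as 81% falling to about 68%. The central prescribing pattern implies 73.6% treated, where power is already 73% before any bias, so that pair mixes two scenarios.

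**Conclusion.** The point holds in conditional form. AF or flutter is not named in the baseline items, the Cox covariates or the strata. Following the plan as written therefore leaves a plausible second indication for the drug outside direct weighting and balance checks.

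If AF raises both prescribing and event risk, AF taken alone understates a benefit or overstates a harm. The uncorrected factor on the risk ratio is 1.015 to 1.19 under the assumed ranges. In the central case it is 1.07, with power falling from about 73% to 59% (56% if both groups are shifted). These are upper bounds for each scenario, since the collected proxies would remove part of the bias, and at the low end the effect is negligible.

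The documents contain no contradiction or wrong figure here. This is a cheap improvement to confounding control, not a demonstrated error in the estimate.

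**What to change.** - In Section 4(f), item a.v, add: *atrial fibrillation or flutter: (a) known before admission, (b) first documented during the index stay before discharge*. Both precede the discharge prescription that defines exposure, so both can serve as baseline covariates.
- In Section 4(g), item b, name AF in the propensity model and in the adjusted Cox covariates, and report its standardized difference after weighting.
- For patients already enrolled, abstract it from the same index-stay EMR.
- Add a sensitivity analysis for remaining unmeasured confounding, for example the bias-factor calculation above over a stated grid. Discharge heart rate, blood pressure and conduction disease are also unlisted, and some of these could bias in the other direction.

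The cost is one more abstracted field with two parts, some retrospective abstraction, and one or two more model terms. No patient contact is needed.

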Gottlieb et al. examined the medical records of more than 200,000 patients with MI as part of the Cooperative Cardiovascular Project (CCP) and found that though beta-blocker use was less common in those with underlying COPD (22% vs. 34%), the overall benefit of beta-blockers on mortality was comparable to that observed in those without COPD (Relative Risk (RR) 0.60; 95%CI, 0.57-0.63).(15) However, no information about the severity of the underlying lung disease was available and the possibility that healthier patients received beta-blockers cannot be excluded. A second study examining data from the CCP did stratify patients with COPD based on whether they were receiving beta-agonists or had been treated with oral steroids or admitted for COPD in the year prior to their MI.(24) In that analysis, COPD patients without these characteristics derived the same mortality benefit from beta-blockers as did patients without COPD (RR 0.85; 95%CI, 0.73-1.00) but no benefit was observed in those treated with beta-agonists or treated for acute symptoms in the year prior. A more recent population-based cohort study from the UK of 1063 patients with COPD and MI occurring between 2003 and 2008 found that treatment with beta-blockers in the hospital, or at the time of discharge, was associated with improved survival compared to no beta-blocker treatment(13). Though this analysis adjusted for COPD severity as assessed by treatment, symptoms and exacerbation history, a large number of patients were excluded as beta-blocker treatment was viewed as contraindicated by the treating physician, in some cases due to COPD. This precludes examination of outcomes in this likely more severely affected group.

The results of our proposed observational study would provide more robust and contemporary data regarding the overall risk-benefit of beta-blockers in COPD patients with acute MI and provide preliminary data about the feasibility of recruitment for a subsequent randomized trial.

3. Specific Aims

Specific Aim 1. To determine the prevalence of COPD in patients admitted to the hospital with an acute myocardial infarction (AMI) and to characterize the phenotypic expression and severity of their underlying lung disease.

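### Key contraindication findings and the reason for withholding a beta-blocker at discharge are not on the index data list, so residual confounding is likely after IPTW and no planned analysis addresses it

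*Combined protocol and SAP*

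**What the plan says.** Section 4(f)(a) lists what is taken from the index admission. For treatment at discharge the entry is "Discharge cardiovascular medications", with no reason attached. Several findings that influence prescribing are on the list: "Initial post MI ejection fraction from inpatient echocardiogram", "Cardiogenic shock during hospital stay", "Need for intubation", and a comorbidity item that includes "diabetes mellitus, cirrhosis, asthma, obstructive sleep apnea". Also listed are heart failure, home oxygen, exacerbations in the prior year, spirometry if it was done in the preceding three years, and respiratory and cardiovascular drugs on admission.

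A reason for a treatment decision is sought only during follow-up (section 4(f)(b)): "Beta-blocker use and reason for discontinuation, if applicable". That covers patients who were taking the drug and stopped, not those who left hospital without it.

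Section 4(g)(b) compares death or all-cause hospitalization at 6 months using weighted survival curves, "while adjusting for the inverse probability of treatment weighting (IPTW) to reduce confounding". The weights are to be informed by the Aim 1 comparison of the two groups, and no fixed covariate list is given for them. No analysis for unmeasured confounding is planned.

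The Background remarks that in one earlier analysis healthier patients may have been the ones treated. It says of another cohort that "a large number of patients were excluded as beta-blocker treatment was viewed as contraindicated by the treating physician".

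**The concern.** The decision that defines the exposure is made at the bedside, partly on findings the protocol does not list: heart rate, blood pressure, conduction block, and bronchospasm or an exacerbation during the stay. If such findings lead to non-prescription and also predict death or readmission, untreated patients will do worse for reasons unrelated to the drug. Weighting on other variables corrects this only so far as those variables stand in for the missing ones.

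Two further things are lost. Unlike the cohort criticised in the Background, this study enrols patients judged contraindicated, but no listed item identifies them, so their outcomes cannot be described separately. Nor can withholding for respiratory reasons, which is the clinical question, be told apart from withholding for haemodynamic or conduction reasons. That distinction also bears on the stated aim of informing the feasibility of a randomized trial.

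**Working it through.** **1. The plan's own figures.** Section 4(g)(c) assumes a 6-month risk of 25% on beta-blockers and 32.5–37.5% off them, with 80% power and 5% type-I error. Table 1 reproduces with Schoenfeld's formula at two-sided 5%. Example cell (37.5% vs 25%, 65% treated):

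- HR = ln(0.75)/ln(0.625) = 0.612
- Events = (1.960 + 0.842)² / [0.65 × 0.35 × (ln 0.612)²] ≈ 143
- Average risk = 0.65 × 0.25 + 0.35 × 0.375 = 0.294
- N ≈ 487, against 488 in the table

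The consent target also follows: 500/(1 − 0.125) = 571.4, stated as 571. The sample-size arithmetic is not in question.

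**2. Planned effect on the risk-ratio scale.** 25/32.5 = 0.77, 25/35 = 0.71, 25/37.5 = 0.67.

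**3. Spurious RR with no drug effect.** Take a binary factor present in a proportion p1 of treated and p0 of untreated patients, multiplying risk by R. The apparent RR is [1 + p1(R − 1)] / [1 + p0(R − 1)]. The documents give none of these inputs. They are assumptions, and should be read as the imbalance remaining after weighting on the collected covariates. With p1 = 5%:

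| p0 | R | Calculation | Spurious RR |
|---|---|---|---|
| 15% | 2 | 1.05/1.15 | 0.91 |
| 15% | 3 | 1.10/1.30 | 0.85 |
| 30% | 2 | 1.05/1.30 | 0.81 |
| 30% | 3 | 1.10/1.60 | 0.69 |

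Three of the four stop short of the weakest planned effect (0.77), and none reaches 0.67. The 0.69 case is demanding: if treated patients average 25%, risk without the factor is 0.25/1.10 = 22.7%, so risk with it is about 68%. With R = 1.5 and p0 = 30% the result is 1.025/1.15 = 0.89.

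**4. What a partial bias does to the test.** In the 0.81 case, 25% in treated patients becomes an apparent 25% × 1.30/1.05 = 31.0% in untreated patients. A pooled two-proportion test at two-sided 5% with 325 treated and 175 untreated rejects about 30% of the time although the drug does nothing. This ignores the extra variance from weighting.

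**5. E-values.** With the RR inverted so that it exceeds 1, E = RR + √[RR(RR − 1)]:

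- 1.30 + √0.39 = 1.92
- 1.40 + √0.56 = 2.15
- 1.50 + √0.75 = 2.37

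To explain a planned effect entirely, an unmeasured factor would need associations of that size with both non-prescription and outcome, over and above the collected covariates.

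**6. Power of a restricted analysis.** Power = Φ(|ln HR| × √[D π(1 − π)] − 1.96), where D is events and π the treated share, at N = 500, 37.5% vs 25%, 65% treated. Suppose 5% of treated patients are excluded and risks among those who remain are unchanged.

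| Untreated excluded | Treated / untreated left | Events | Power |
|---|---|---|---|
| none (and no treated excluded) | 325 / 175 | 147 | 81% |
| 20% | 309 / 140 | 130 | 74% |
| 30% | 309 / 122 | 123 | 69% |
| 40% | 309 / 105 | 117 | 64% |

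**The case against.** A good deal can be said for the plan. Many drivers of prescribing are collected and can enter the weights. The secondary models adjust for oxygen, prior COPD hospitalizations and low ejection fraction, and stratification by asthma and admission beta-blocker use is planned if numbers allow. The protocol promises only to reduce confounding, frames Aim 2 as an association, and acknowledges that observational data cannot settle cause and effect. It also answers one Background criticism directly, since contraindicated patients are not excluded.

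All of that stands, and it rules out some stronger conclusions a reader might draw:

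- *The findings behind the decision are not collected.* Too broad. Specific items are missing; others are listed.
- *The case report form lacks these fields.* The form is not among the documents. Only the protocol's list can be judged.
- *Confounding by contraindication would account for the planned effect, or would make the drug look better.* Not shown. The prevalences and risk ratios are assumed, and most combinations fall short. Direction is uncertain because indications and contraindications pull opposite ways: low ejection fraction or heart failure may favour prescribing.
- *The study repeats the UK cohort's flaw.* That cohort excluded contraindicated patients. This one includes them but has no item to identify them.

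One line under follow-up says records will be gathered for every admission. If that includes the index stay, later abstraction might be possible, but no data element is defined for it.

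What the objection does not answer is that the missing items are ordinary chart data, the weights cannot use them unless they are collected, and no planned analysis asks how much their absence matters.

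**Conclusion.** The point holds in a limited form. The protocol's index list omits discharge heart rate, systolic blood pressure, second- or third-degree AV block, bronchospasm or exacerbation during the stay, and the reason for no beta-blocker. Residual confounding by contraindication in the primary comparison is therefore likely and partly avoidable. Its size is unknown. Under the assumed inputs the distortion runs from slight (0.91) to comparable with the planned effect (0.69), and even a mid-range case could raise the false-positive rate well above 5%. These figures show that the matter deserves attention; they do not estimate the bias. The study can proceed without the change, but the change is worth making because a protective association would otherwise be open to the healthier-patient criticism that the Background makes of earlier work.

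**What to change.** - Add to the index EMR abstraction, for treated and untreated patients alike: last heart rate and systolic blood pressure before discharge, second- or third-degree AV block, and bronchospasm or COPD exacerbation during the stay.
- Name these findings in advance as propensity-model covariates, rather than leaving their entry to the Aim 1 comparison.
- Record the documented reason for no beta-blocker (respiratory, haemodynamic, conduction, other, none stated) for description only. It exists only in untreated patients, so it cannot be a propensity covariate. Using it as an exclusion rule would remove sick untreated patients while keeping treated patients with the same findings.
- Prespecify a sensitivity analysis that excludes patients in both groups who meet one findings-based definition of a non-respiratory contraindication, with that definition set by the investigators before outcome data are examined. This also helps where patients with a finding are almost never treated, a problem weighting cannot solve.
- Report an E-value or similar bias analysis with the primary result.

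The cost is modest abstraction time in an EMR review already done under all three enrolment options, with no new visit or test. Some values will be missing and need a stated handling rule. The restricted analysis loses power, for example from 81% to about 74–64% under the assumptions shown, which is acceptable for a sensitivity analysis.

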Patients admitted to the hospital and who undergo cardiac catheterization for an AMI will be identified through the electronic medical record (EMR). Those with a diagnosis of COPD in the EMR will be offered participation in the study. Baseline characterization will include demographics, smoking history, prior history of exacerbations in the year before admission, supplemental oxygen use, respiratory and cardiac medication use, comorbidities including history of coronary artery disease, heart failure and ejection fraction, and pulmonary function data as available in the EMR. Results of this Aim will provide data about the prevalence and clinical characteristics of COPD in the hospitalized population with AMI in our network. The Aim will also provide an estimate of the number of annual admissions for patients with COPD and AMI.

Specific Aim 2. To determine the association between beta-blocker use at discharge and cardiopulmonary outcomes in patients with COPD and AMI.

Patients with AMI and EMR-documented COPD will be followed, prospectively from the time of discharge using review of the electronic medical record and as local guidance permits, phone calls at 3 and 6 months. We will determine the associations between beta-blocker use at discharge and the risk for all-cause mortality, recurrent ischemic events, and hospitalization for COPD exacerbation adjusting for baseline characteristics and COPD severity.

4. Study Design and Methods

- a) **Overview.** The study is a prospective, observational study of patients admitted to the BLOCK COPD network hospitals with acute AMI and COPD. Patients with will be identified via the EMR. Because of the current COVID-19 pandemic and the possibility of limited access to hospitalized patients, the study consists of three options for enrollment. Option 1 or 2 is preferable if local guidance permits.

Option 1: A total of 3 visits including 1 in person visit in the hospital and 2 follow up phone calls with EMR review at 3 and 6 months after discharge. Sites may consider alternatives to in person consent and data collection including by telephone or video conference.

Option 2: EMR review at the time of hospital admission followed by post-discharge telephone consent and 2 follow up phone calls with EMR review at 3 and 6 months.

Option 3: EMR review at the time of hospital admission and follow-up review of the EMR at 3 and 6 months after discharge.

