b) **Participant selection and eligibility.** Subjects hospitalized and who undergo cardiac catheterization with AMI and have EMR-documented COPD will be eligible for participation. The age, race, gender, smoking status and comorbidities of patients with who undergo cardiac catheterization for AMI but have no EMR-documented diagnosis of COPD will be recorded but no other information will be collected on this population.

c) **Inclusion Criteria**

- a. Willing and able to provide informed consent (applicable for Option 1 and 2 only)
- b. Men and women age 35 or older
- c. Admitted to hospital from the Emergency Department or by hospital to hospital transfer with a primary diagnosis of AMI
- d. Undergo cardiac catheterization for AMI
- e. EMR-documented COPD

d) **Exclusion Criteria**

- a. Cognitive disorder that in the judgment of the investigator impairs understanding of the study objectives or assessments (applicable for Option 1 only)
- b. Vulnerable populations, including prisoners and pregnant women

e) **Consent Process.** Patients admitted and who undergo cardiac catheterization for AMI will be identified via the EMR. If protocol Option 1 is being followed those with EMR-documented COPD will be approached for participation. They will be asked to provide written consent only after the objectives and risks of the study have been fully explained. Surrogate consent will not be permitted. The reasons for patients not being eligible for the study will be recorded. If protocol Option 2 is being followed a waiver of informed consent will be obtained from local IRBs for the initial EMR review and then telephone consent will be obtained after discharge. If Option 3 is being followed a waiver of consent will be obtained.

f) **Study Visit Schedule and Assessments**

- a. In-hospital visit and EMR review. All data elements will be obtained from the EMR except the self-reported COPD assessment which will be obtained during the hospitalization and after informed consent in protocol Option 1 and after discharge and phone consent in protocol option 2.
 - i. Demographics to include age, gender, race and ethnicity, height, weight
 - ii. Smoking status

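### The protocol contradicts itself on whether Option 2 participants are called at 3 and 6 months, and the primary analysis does not name enrollment option although it determines how endpoint events are found

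*Combined protocol and SAP*

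**What the plan says.** Section 4.a sets out three enrollment options.

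- Option 1 has an in-hospital visit, then two calls with EMR review.
- Option 2 has "post-discharge telephone consent and 2 follow up phone calls with EMR review at 3 and 6 months".
- Option 3 is "EMR review at the time of hospital admission and follow-up review of the EMR at 3 and 6 months after discharge", with no call.

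The choice depends on local circumstances: "Option 1 or 2 is preferable if local guidance permits".

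Section 4.f.b, which lists what is collected at follow-up, is headed "Phone calls (Option 1 only) and EMR review at 3 and 6 months". Its items include vital status, date of death and interval hospitalization. On hospitalization it says "all events will be captured but hospitalizations for COPD exacerbations, recurrent MI, revascularization, or heart failure will be specifically queried", and it adds "Medical records will be collected for all admissions".

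Section 4.g.b makes death or all-cause hospitalization at 6 months the primary endpoint. It is analysed with weighted Kaplan–Meier curves and an adjusted log-rank test. The weights are to be informed by the Aim 1 comparison of clinical characteristics. Enrollment option appears in neither the description of the weights, the log-rank test, the Cox covariates nor the stratification factors. Site is a stratification factor, but only if frequencies are adequate, and that sentence refers to the models.

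**The concern.** There are two linked problems.

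The first is a plain contradiction. A site working from 4.a would call its Option 2 participants; a site working from 4.f.b would not. The Aim 2 text in section 3 makes calls depend on local guidance without naming an option, so it does not settle the matter.

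The second remains once the first is corrected. Some participants are asked about admissions and others are followed through the record alone. The commitment to capture all events and collect all admission records helps only for admissions the study learns of. The protocol gives no means of learning of an admission outside the EMR when nobody calls.

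If events are missed without a call, power falls. If the mix of options also differs between beta-blocker groups, the groups are observed with different sensitivity, and the comparison can be biased in either direction.

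**Working it through.** **Inputs from section 4.g.c.** Target 500 discharged alive; 6-month risk 25% on beta-blockers and 32.5–37.5% off; 45–85% discharged on beta-blockers; 80% power; 5% type I error (taken as two-sided).

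**Reproducing the plan's figure.** Take HR = ln(1−r1)/ln(1−r0), with r1 the treated and r0 the untreated risk. Schoenfeld events are (1.960+0.842)²/[p(1−p)(ln HR)²], with p the treated share. For 25% vs 37.5% and p=0.65:

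- HR = ln(0.75)/ln(0.625) = 0.612
- events = 143.2
- overall risk = 0.65×0.25 + 0.35×0.375 = 0.29375
- N = 143.2/0.29375 = 487.4, rounded up to 488, the Table 1 entry

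The same method reproduces all of Table 1 within 3% or 2 patients, so it is used below.

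**Assumptions not in the documents.** The share q of events missed without a call, the option mix and any prescribing gap are all assumed. The planned risks are taken as true risks. If they are as-observed risks, the power loss is already included.

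**Power.** With one third of patients per option, the overall missed share is m = q/3 if Option 2 is called and m = 2q/3 if it is not. Both risks are multiplied by (1−m). With N=500 and p=0.65, expected events are 500×(0.65×r1 + 0.35×r0), and power is Φ(√(events×0.65×0.35)×|ln HR| − 1.960).

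| Untreated risk | q | Option 2 called | Option 2 not called |
|---|---|---|---|
| 37.5% | 0 | 81.0% | 81.0% |
| 37.5% | 10% | 79.0% | 77.0% |
| 37.5% | 20% | 77.0% | 72.6% |
| 37.5% | 30% | 74.8% | 67.9% |
| 35% | 0 | 63.3% | 63.3% |
| 35% | 20% | 59.0% | 54.7% |

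At q=20% and 37.5%, for example, events fall from 146.9 to 137.1 (called) or 127.3 (not called). At 32.5% untreated risk, full-capture power is 41.7%.

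**Bias with no true effect.** Assume 30% risk in both groups, half the patients in Option 1 and half in Option 3, a share m of events missed in Option 3, and option ignored. If 85% are treated in Option 3 and 65% in Option 1, the Option 3 share is 0.85/1.50 = 0.567 of the treated and 0.15/0.50 = 0.300 of the untreated. Observed risk is 0.30×(1 − m×share). At m=30% this gives 24.9% treated and 27.3% untreated, HR 0.898. Type I error uses the shift √(events×0.75×0.25)×ln HR with N=500.

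| Treated, Option 3 / Option 1 | HR at m = 10%, 20%, 30% | Type I error |
|---|---|---|
| 80% / 70% | 0.98, 0.97, 0.95 | 5.1%, 5.3%, 5.8% |
| 85% / 65% | 0.97, 0.93, 0.90 | 5.3%, 6.4%, 8.2% |
| 70% / 80% | 1.02, 1.04, 1.06 | similar to 80/70 |
| 65% / 85% | 1.03, 1.07, 1.12 | similar to 85/65 |
| equal | 1.00 | 5% |

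**Simulation check.** This used 8,000 trials per cell, N=500 and no other confounders. Ignoring option gave type I error of 4.9–6.0% (80/70) and 5.5–9.0% (85/65). Stratifying the log-rank test by option gave 4.6–5.0%, and including option in stabilised weights gave 4.6–5.5%, with HR about 1.00 throughout. With a true effect (37.5% vs 25%) and 20% missed in Option 3, the stratified test rejected in 75–77% of trials, against 81–82% with full capture. Adjustment removes the bias but does not recover missed events.

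**The case against.** The heading of 4.f.b is probably out of date. Section 4.a is explicit, and the cognitive-disorder exclusion in 4.d is also tagged for Option 1 only although Option 2 requires consent, so other labels may not have been updated. On that reading the contradiction is a small wording correction, and the "not called" power figures describe a study nobody intends.

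The bias needs both material under-capture by EMR and an association between option and prescribing, and the documents establish neither. With a 10-point prescribing gap the type I error is at most 5.8%, which is negligible. The assumed miss rates apply to the whole composite, deaths included. A participant is wrongly event-free only if every qualifying event is missed, and EMR review applies in all options. The inputs to the weights are not a closed list, and site stratification could absorb much of an option effect. Uncertainty about the untreated risk matters more for power: 37.5% to 35% takes it from 81% to 63%.

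All of this limits the weight of the point. It does not remove it. The text as written still tells sites two different things. Option 3 has no call on any reading, so unequal ascertainment survives the correction. Site stratification is conditional, is written for the models rather than the primary test, and would not cover a site that changes option.

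**Conclusion.** The concern holds, as something the sponsor should correct. The contradiction is in current operative text. The difference in ascertainment, and the absence of option from the stated primary analysis, are clear from the protocol.

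The consequence cannot be sized from the documents. If 20–30% of events are missed without a call and options are equally used, leaving Option 2 uncalled costs about 4 to 7 points of power in the most favourable planned scenario (77.0% to 72.6%; 74.8% to 67.9%). Bias arises only if option and prescribing are associated. It is negligible for a 10-point gap. For a 20-point gap with 20–30% missed, the null HR moves to 0.93–0.90 or 1.07–1.12, with type I error of about 6–8% by formula and up to 9% in simulation.

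**What to change.** 1. Reconcile 4.a and 4.f.b on whether Option 2 participants receive the 3- and 6-month calls. Which text stands is for the sponsor to decide.
2. Name enrollment option in the propensity model, or stratify the primary weighted log-rank test by it, adding site only if frequencies allow. State that this removes between-option distortion but does not recover missed events.
3. Report numbers and follow-up completeness by option and beta-blocker group, with a supportive analysis by option. State that Options 1 and 2 require consent, and that in Option 2 "then telephone consent will be obtained after discharge", so differences between options may reflect selection rather than event capture. If the source of each event is recorded, an analysis restricted to EMR-found events in all options would be a direct check on unequal capture.
4. As a minor clarification, state that censoring before 6 months applies at withdrawal or documented loss to follow-up.

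The cost is one line of text, one three-level variable known at enrollment, one table and one supportive analysis. Even with 85% treated, 500 patients include 500×0.15 = 75 untreated, about 25 per option if options are equally used, so three strata are workable. Option crossed with site may be too sparse.
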